Appendix 13. Peak Pruritus-Numeric Rating Scale

The PP-NRS is a scale used to quickly assess itch/pruritus severity over a 24-hour period which will be used daily to assess peak pruritus.

For subjects ages 2 to < 12 years, the PP-NRS will be completed by the caregiver. For subjects ages ≥ 12 years, the PP-NRS will be completed by the subject.

PP-NRS

On a scale of 0 to 10, with 0 being 'no itch' and 10 being 'worst itch imaginable', how would you rate your itch at the worst moment during the previous 24 hours?

PP-NRS © 2019 Regeneron Pharmaceuticals, Inc. and SAR&D. All rights reserved. Used with permission of Regeneron Pharmaceuticals, Inc. and SAR&D

Dermavant	Dermavant Sciences, Inc.
EASI	Eczema Area and Severity Index
EOS	End of Study
EOT	End of Treatment
ICH	International Council for Harmonisation
ITT	Intent-to-Treat
LOCF	last observation carried forward
MedDRA	Medical Dictionary for Regulatory Activities
OC	observed cases
OL-LTE	Open-Label, Long-Term Extension study
PK	Pharmacokinetic(s)
PP-NRS	peak pruritus-numeric rating scale (daily itch score)
PT	preferred term
QC	quality control
QD	once daily

Abbreviation	Full Notation
RTF	rich text format
SAE	serious adverse event
SAP	Statistical Analysis Plan
SAS®	Statistical Analysis Software
SBP	systolic blood pressure
SD	standard deviation
SOC	System organ class
TEAE	Treatment-emergent adverse event
TLFs	Tables, listings, and figures
VAS	visual analog scale
vIGA-AD™	validated Investigator Global Assessment for Atopic Dermatitis
WHO-Drug Global	World Health Organization Global Drug Dictionary

1. INTRODUCTION

This document outlines the statistical methods to be implemented during the analyses of data collected within the scope of DMVT-505-3103 [An Open-Label, Long-Term Extension Study to Evaluate the Safety and Efficacy of Tapinarof Cream 1% in Subjects with Atopic Dermatitis]. The purpose of this plan is to provide specific guidelines for the statistical analyses. Any deviations from this plan will be documented in the clinical study report (CSR).

2. STUDY DOCUMENTS

The following study documents are used for the preparation of the Statistical Analysis Plan (SAP):

- Protocol, Version 2.0, 16JUN2021
- Annotated case report form (CRF), Version 1.0, 09SEP2021.
- Data management plan, Version 1, 08OCT2021.

3. STUDY OBJECTIVES

- To evaluate the safety and tolerability of tapinarof cream, 1% in subjects with atopic dermatitis (AD)
- To evaluate the efficacy of tapinarof cream, 1% over an extended period of time in subjects with AD
- To describe the effect of tapinarof cream, 1% on AD symptom severity and the associated impact on daily activities and attitudes in subjects with AD

4. STUDY DESIGN AND PLAN

This is an open-label, long-term multicenter, study to evaluate the safety and efficacy of topical tapinarof cream, 1% in subjects with AD. Subjects in this study will have either: a) completed treatment with tapinarof or vehicle in one of two Phase 3 pivotal safety and efficacy studies, DMVT-505-3101 or DMVT-505-3102, and rolled over into this study; b) completed treatment with tapinarof in the Phase 2 maximal use PK study, DMVT-505-2104, and rolled over into this study; or c) enrolled directly into this study. This study will consist of up to 48 weeks of treatment and a 1-week safety follow-up period.

At the completion of the Week 8 visit of study DMVT-505-3101 or study DMVT-505-3102 or the Day 28 visit of study DMVT-505-2104 (Baseline [Day 1] in this study), all eligible subjects will be offered enrollment in this open-label, long-term extension (OL-LTE) study.

Approximately 125 additional pediatric subjects ages 2 to <18 years who are not eligible for participation in the Phase 3 pivotal studies (DMVT-505-3101 or DMVT-505-3102) will be enrolled directly into this OL-LTE study. Study visits during the treatment period for all subjects will occur every 4 weeks (± 3 days). Unscheduled visits may occur, as needed. Subjects who withdraw from the study before Week 48 will return to the study site for an Early Termination

visit. The total duration of subject participation in this study will be approximately 49 weeks for rollover subjects (Baseline to Follow-Up) and approximately 53 weeks for direct-enrolling subjects (Screening to Follow-Up).

Rollover subjects in this study will begin treatment based on their validated Investigator Global Assessment for Atopic Dermatitis (vIGA-ADTM) score from the final visit in one of the three aforementioned studies (DMVT-505-3101, DMVT-505-3102, or DMVT-505-2104). Subjects entering with a vIGA-ADTM ≥ 1 will receive treatment with tapinarof cream, 1% once daily (QD) until they achieve a vIGA-ADTM score of 0, at which time treatment will be discontinued and subjects monitored for maintenance of disease control (i.e., the extent of the remittive effect). If/when disease worsening occurs, as evidenced by a flare to vIGA-ADTM ≥ 2 , treatment will then be re-initiated and continued until a vIGA-ADTM of 0 is achieved. Subjects entering with a vIGA-ADTM of 0 will have treatment discontinued beginning at the Baseline visit and will be monitored for maintenance of the remittive effect. If/when disease worsening occurs, as evidenced by a vIGA-ADTM ≥ 2 , treatment will then be re-initiated and continued until a vIGA-ADTM of 0 is achieved. This treatment and re-treatment pattern of use will be continued until the end of the study (i.e., subjects may receive study treatment up until the Week 48 visit).

Subjects enrolling directly into this study will receive treatment QD with tapinarof cream, 1% beginning at Baseline and continue treatment until they achieve a vIGA-ADTM score of 0, at which time treatment will be discontinued and subjects monitored for maintenance of the remittive effect. If/when disease worsening occurs, as evidenced by a flare to vIGA-ADTM ≥ 2 , treatment will be re-initiated and continued until a vIGA-ADTM of 0 is achieved. This regimen of treatment and re-treatment will continue until the end of the study (i.e., subjects may receive study drug up until the Week 48 visit).

Study drug will be dispensed to subjects or their caregivers, applied during the clinic visits, and applied at home between clinic visits as instructed by site personnel. Subjects or their caregivers will be instructed to apply study drug QD to all affected areas, including newly appearing lesions and lesions/areas that improve during the study until a vIGA-ADTM of 0 is achieved. Once a vIGA-ADTM of 0 is achieved, the treatment period ends. If/when disease worsening occurs, and treatment is re-initiated at a vIGA-ADTM of ≥ 2 , all lesions currently present and any new lesions that occur during the new treatment period should be treated.

Subjects or their caregivers will apply sufficient study drug to cover each lesion completely with a thin layer of study drug and will record the time of study drug application and daily itch score (PP-NRS) in a daily diary provided by the study site. Subjects are allowed, but not required, to treat scalp lesions with study drug; however, efficacy analyses will not include assessment of AD on the scalp. At the first clinic visit, if applicable, subjects and/or caregivers will be instructed to maintain the approximate dosing time for the daily application of study drug. At the phone contact at Week 2, subjects or caregivers should be reminded to complete their daily diary and bring it with them to the next clinic visit.

Study drug application instructions will be reviewed at all post-randomization clinic visits and during any planned study phone calls. On clinic visit days, subjects and/or caregivers will be instructed/reminded on how to apply study drug (except during the final treatment/end-of-study visit). During the clinic visits, subjects or their caregivers will apply the daily dose of study drug while on-site under the supervision of site personnel, after efficacy and safety assessments have been completed (except for Local Tolerability Scale [LTS] at Week 4 through Week 44). The time of the dose application and assessments will depend on the time of the clinic visit. Therefore, the timing of the clinic visit may lead to a change in the subject's chosen dosing time for that day.

Safety assessments will include Adverse Events (AEs), clinical laboratory tests, physical examination, vital signs, and [REDACTED]. Efficacy assessments will include vIGA-AD™ score, percent of body surface area (%BSA) affected, Eczema Area and Severity Index (EASI), Peak Pruritus-Numeric Rating Scale (PP-NRS), [REDACTED]
[REDACTED]
[REDACTED]

Refer to Protocol Section 6 for descriptions of study procedures and assessments and Protocol Section 7 for timing of procedures and assessments.

5. DETERMINATION OF SAMPLE SIZE

The sample size of this study is based on the International Council for Harmonisation (ICH) E1A guideline on extent of population exposure to assess clinical safety for drugs intended for long term treatment of non-life-threatening conditions. Up to 961 subjects will be enrolled in this study across all regions, including up to 836 rollover subjects from studies DMVT-505-3101, DMVT-505-3102, and DMVT-505-2104 and approximately 125 subjects directly enrolling into this study.

6. GENERAL ANALYSIS CONSIDERATIONS

The statistical analyses will be reported using summary tables, listings, and figures (TLFs). The ICH numbering convention will be used for all TLFs. The efficacy and safety results from this study will be summarized descriptively. There will be no statistical testing.

Continuous variables will be summarized by presenting the number of observations, means, standard deviations, medians, minimums, and maximums.

Categorical variables will be summarized by presenting counts and percentages of subjects in corresponding categories. All possible categories as defined in the CRF should be populated, even if they have zero counts. Percentages for missing values are omitted and do not account for the percent calculation of other categories. Percentages are based on the total category count

excluding the missing category if not otherwise mentioned. In certain tables (e.g., treatment-emergent adverse events [TEAE]), the total number of subjects is used as denominator. Footnotes will specify the percent basis in those cases.

Data will be summarized by the following categories: received tapinarof treatment in pivotal study; received vehicle treatment in pivotal study; total pivotal; received tapinarof treatment in maximal use study; enrolled directly; and overall total.

Individual subject data obtained from the CRFs, external vendors, central clinical laboratory, and any derived data will be presented by subject in data listings.

The analyses described in this plan are considered a priori, in that they have been defined before database lock.

All analyses and tabulations will be performed using SAS® software Version 9.4 or higher. Tables, listings, and figures will be presented in RTF format.

The process for SAS program validation and quality control (QC) for programs and outputs is documented in the Synteract working instruction “SAS programming quality control.” Study-specific QC requirements can be found in [Appendix B: SAS programming QC requirements](#).

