10.5 Interim Analyses

A data-cut will be made at the time of preparation of the marketing application to present interim results; the final analysis will be conducted after study completion (e.g., the last subject's last visit).

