8. ANALYSIS SETS

The following subject population will be used for safety and efficacy analyses:

- The intent-to-treat (ITT) population will include all subjects enrolled into the study.

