10.5 Interim Analysis and Data Monitoring

An interim analysis will be performed to review safety data after at least 100 pediatric subjects (<18 years of age) have reached 48 weeks of potential active study drug treatment, inclusive of active study drug treatment in one of three parent (i.e., pivotal and maximal use) studies. All summaries will be produced for interim analysis.

The final analysis will be conducted after study completion (i.e., the last subject's last visit) and database lock.

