13. SAFETY ANALYSES

All safety analyses will be based on the ITT population. Definition of baseline values is outlined in section 10.2.

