AEs resolved prior to the Visit 1 date, Serious TEAEs, TEAEs leading to study drug discontinuation, TEAEs leading to study discontinuation and TEAEs related to study drug will also be listed separately. The following AESIs will be identified and listed separately: contact dermatitis, follicular event, and headache.

The frequency and percent of subjects with AEs will be summarized as incidence rates of:

- Any AE

The frequency and percent of subjects with TEAEs will be summarized as incidence rates of:

- Any TEAE
- Any TEAE excluding those ongoing at the end of the previous studies
- Any TEAE ongoing at the end of the previous studies
- Any treatment-emergent AESIs
- Any treatment-emergent AESIs excluding those ongoing at the end of the previous studies
- Any treatment-emergent AESIs ongoing at the end of the previous studies
- Any treatment-related TEAE
- Any TEAE leading to study drug discontinuation
- Any TEAE leading to study discontinuation
- Any serious TEAE
- Death
- Treatment-related serious TEAE
- Serious TEAE leading to study drug discontinuation
- Serious TEAE leading to study discontinuation
- TEAE (COVID-19)

TEAEs will be sorted alphabetically by SOC and decreasing PT frequency in the Total (Overall) group for the following:

- All TEAEs
- All TEAEs by maximum CTCAE grade

- All TEAEs by maximum causality (not related, related) to the study drug
- All TEAEs excluding those ongoing at the end of the previous studies
- All TEAEs ongoing at the end of the previous studies
- All treatment-related TEAEs
- All TEAEs leading to study discontinuation
- All TEAEs leading to study drug discontinuation
- All serious TEAEs
- All serious TEAEs leading to study discontinuation
- All serious TEAEs leading to study drug discontinuation

All TEAEs and all serious TEAEs will also be summarized by SOC (alphabetical order) and PT (descending order) for the following subgroups:

- Age (2-6 yrs, 7-11 yrs, 12-17 yrs, ≥ 18 yrs)
- Sex
- Race (White, Asian, Black or African American and Other)

TEAEs by maximum CTCAE grade, TEAEs by maximum causality, TEAEs leading to study drug discontinuation and TEAEs leading to study discontinuation, will be summarized by SOC (alphabetical order) and PT (descending order) for the Age subgroup.

Furthermore, TEAEs will be categorized by day of onset among the following 4 categories:

- ≤ 12 weeks
- > 12 to ≤ 24 weeks
- > 24 to ≤ 48 weeks
- > 48 weeks.

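### The TEAE-by-onset-window table uses all enrolled subjects as denominator in every window, so later-window incidence is understated and the unequal windows cannot be compared

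*SAP*

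**What the plan says.** SAP section 6 sets the rule. For certain tables, with TEAE tables as its example, it says "the total number of subjects is used as denominator". It adds that footnotes will state the percent basis. SAP section 13 says "All safety analyses will be based on the ITT population", and SAP section 8 defines that set: "The intent-to-treat (ITT) population will include all subjects enrolled into the study". Membership carries no dosing or follow-up condition.

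SAP 13.2 then says "TEAEs will be categorized by day of onset among the following 4 categories": up to 12 weeks, over 12 to 24, over 24 to 48, and over 48 weeks. Each category is tabulated by system organ class and preferred term. No at-risk count, person-time or exposure-adjusted rate is specified for any window.

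Three other provisions bear on the table:

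- Protocol 6.2.1 collects adverse events only up to the subject's last visit or contact, and Protocol 4.5 does not replace withdrawn subjects.
- SAP 10.5 triggers an interim once at least 100 children have reached 48 weeks of potential active treatment, counting parent-study treatment, and says "All summaries will be produced for interim analysis". The onset-window table is therefore included.
- Protocol 10.5 says "A data-cut will be made at the time of preparation of the marketing application to present interim results".

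**The concern.** The study exists to describe long-term safety, and its size rests on the ICH E1A exposure guideline. Of the TEAE tables in the unredacted text, this is the one that shows when events of all kinds begin. A reader will use it to judge whether events emerge or accumulate with continued use.

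With all enrolled subjects in every denominator, a subject who left at Week 10 counts as event-free in the >24–48 week window, although nobody was collecting that subject's events. At the interim the same applies to a subject with only 10 weeks of follow-up so far. Later-window incidence is understated in proportion to the follow-up that is missing.

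Unequal window widths add a second distortion. The third window is twice as wide as each of the first two, and the fourth is about one week. Width raises the >24–48 week percentage while lost follow-up lowers it, so the printed figure reflects both and cannot be set beside its neighbours.

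**Working it through.** **Plan's own figure.** 836 rollover + 125 direct = 961, the maximum enrolled and so the largest possible denominator of the overall column. The study is descriptive, so there is no power calculation to reproduce.

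**Inputs.** The window limits come from SAP 13.2; planned follow-up ends at Week 49. Dropout, accrual period and share of children are not in the documents, so the values below are assumptions.

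**Final analysis: follow-up.** Assume exponential dropout reaching *d* by Week 48, so *h* = −ln(1 − *d*)/48 and *S(t)* = exp(−*ht*).

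- Share in the study when the >24–48 week window opens: *S*(24) = √(1 − *d*).
- Average share observed across it: [*S*(24) − *S*(48)]/(24*h*).

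For *d* = 15%, *h* = 0.003386. *S*(24) = 0.922 (886 of 961), so 7.8% are gone. The average is (0.92195 − 0.85)/0.08126 = 0.8855, so 11.5% is unobserved.

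For *d* = 45%, *h* = 0.012455. *S*(24) = 0.742 (713 of 961), so 25.8% are gone. The average is (0.74162 − 0.55)/0.29892 = 0.641, so 35.9% is unobserved.

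**Final analysis: what the table would print.** Assume a constant event hazard of 10% per 12 weeks: λ = −ln(0.9)/12 = 0.00878 per week. For a window starting at *a* with length *L*, the percentage over all enrolled is *S(a)* × λ/(λ + *h*) × [1 − exp(−(λ + *h*)*L*)]. Dropping *S(a)* gives the window-start version.

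| Case | ≤12 | >12–24 | >24–48 | >48 (1 week) |
|---|---|---|---|---|
| No dropout | 10.00% | 10.00% | 19.00% | 0.87% |
| 15% dropout, all enrolled | 9.80% | 9.41% | 16.85% | 0.74% |
| 15% dropout, window start | 9.80% | 9.80% | 18.27% | 0.87% |
| 45% dropout, all enrolled | 9.30% | 8.01% | 12.24% | 0.48% |
| 45% dropout, window start | 9.30% | 9.30% | 16.51% | 0.87% |

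Three things follow.

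- Dropout lowers the all-enrolled >24–48 week figure from 19.00% to 16.85%–12.24%.
- That figure still exceeds both earlier windows because its window is twice as wide.
- The window-start denominator recovers only part of the loss (18.27%–16.51%) and leaves the widths unequal.

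First events divided by time at risk in the window return λ in every window: 0.00878 × 52.18 weeks = 45.8 per 100 subject-years, whatever the dropout or width.

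**Interim.** Assume uniform enrolment of 961 over *A* weeks, 50%–80% children (*c*), 20%–35% dropout by Week 48, and 0 or 8 weeks of parent-study credit, so *w* = 48 or 40 extension weeks are needed. Requiring the 100 children still to be in the study puts the cut at *T* = *w* + *A* × 100/[961 × *c* × *S(w)*]. The share observed at extension week *t* is *S(t)* × min{1, max[0, (*T* − *t*)/min(*T*, *A*)]}, averaged over weeks 24–48.

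- *A* = 40–80. Lowest: *A* = 40, *c* = 0.8, 35% dropout, 8 weeks' credit. *S*(40) = 0.698, *T* = 40 + 40 × 0.186 = 47.4, average 22%. Highest: *A* = 40, *c* = 0.5, 20% dropout, no credit. *T* = 48 + 40 × 0.260 = 58.4, average 48%.
- *A* = 20. The same two settings give *T* = 43.7 and 53.2, with averages of 31% and 66%.

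The SAP says potential treatment. If children who have dropped out also count towards the 100, *S(w)* is replaced by 1, and the 22%–48% range becomes 18%–43%.

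**The case against.** Several counter-arguments have weight.

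- **The rule is general.** SAP 6 speaks of certain tables and gives TEAE tables as an example; no sentence assigns a denominator to the onset table by name. That is fair, but TEAE tables are the named example and nothing unredacted overrides it here. The promised footnote would disclose the basis without showing how many subjects were followed in each window.
- **Censoring is handled elsewhere.** SAP 13.2 plans Kaplan-Meier figures of time to first event for contact dermatitis, follicular event and headache. SAP 9.1 plans a Kaplan-Meier curve of days in study, and every TEAE is listed with its onset date. This is real mitigation, but it covers only the three events of special interest and leaves the all-TEAE table as it is.
- **The percentage is valid as a share of all enrolled subjects with onset in that window,** and no testing is planned. Both are true. That share is not late-onset risk, however, and late-onset risk is what a table split by onset time will be taken to show.
- **A reader might infer that the table must show falling incidence even when the true rate is constant.** For the final table this is not so. With a constant hazard, the >24–48 week percentage is the highest of the four at both 15% and 45% dropout. The >48 week figure is small mainly because that window is about one week wide.
- **A reader might infer a severe interim distortion as fact,** for example that only 100 of 961 subjects have entered a late window. The trigger is a minimum, and the documents give no accrual period, share of children or dropout rate.

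**Conclusion.** The point holds. On the direct reading of SAP 6, 8, 13 and 13.2, every onset window is divided by all enrolled subjects, so those who have left or have not yet arrived count as event-free. The understatement is present whenever follow-up is incomplete; with full retention at the final analysis it disappears.

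Its size rests on assumptions. With 15%–45% dropout by Week 48, 8%–26% of enrolled subjects are gone at the start of the >24–48 week window, and 11.5%–35.9% are unobserved on average across it. The first range is what a window-start denominator corrects; the second is the whole shortfall.

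At the interim, roughly 22%–48% of enrolled subjects are observed on average across that window with 40–80 weeks of uniform enrolment, and 31%–66% with 20 weeks. These are illustrations. Protocol 10.5 links a data cut to the marketing application, so the interim version may be the one that is read most closely.

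The conclusion is that raw percentages in this table cannot be compared across windows or read as late-onset risk. It does not extend to a particular direction of trend in the printed figures.

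**What to change.** In SAP 13.2, for the onset-window table at both interim and final:

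1. Print the number of subjects under observation at the start of each window in the column header, and base that window's percentages on it.
2. Add the exposure-adjusted rate: subjects with a first event in the window per 100 subject-years followed in that window, with time counted up to that first event, study exit or the data cut. This is needed as well as item 1, because a window-start denominator does not correct partly observed or unequal windows.
3. Say in SAP 6 that this table is an exception, and keep total N for the overall TEAE tables.

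The cost is SAP wording and a few derived variables from visit, onset and discontinuation dates already collected. No new data are needed. Late-window percentages will be somewhat higher than under the present rule.
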